Modulating interaction of motor learning networks in rehabilitation of stroke

NCT03086551

January 10th, 2018

SPECIFIC AIMS

Aim 1: Determine whether cTBS over contralesional dorsolateral prefrontal cortex prior to motor practice enhances motor learning post-stroke. Aim 1 will compare the efficacy of contralesional cTBS over dorsolateral prefrontal cortex paired with motor practice versus sham cTBS paired with practice for improving motor function.

Aim 2: Determine the effects of cTBS over dorsolateral prefrontal cortex upon motor networks. Our second aim is to determine the effect of our cTBS intervention upon local intracortical networks within primary motor cortex and across the motor network.

Aim 3: Provide preliminary evidence for individual predictors of the efficacy of dorsolateral prefrontal cortex cTBS post-stroke. Within our exploratory third aim, we will examine the relationship between pre-intervention behavioral and brain metrics and the responsiveness to dorsolateral prefrontal cortex cTBS.

RESEARCH STRATEGY

Design

Aims 1, 2 and 3 will be assessed in a single experiment. 16 individuals with first time middle cerebral artery (MCA) territory ischemic stroke will serve as their own matched control in a cross-over design. Each arm of the cross-over design will include the same 6 sessions (Figure 1). Each session within an arm of the cross-over design will be separated by at least 24 hours and the duration of each arm will not exceed three weeks. The only difference between the arms of the study will be the delivery active cTBS or sham cTBS over dorsolateral prefrontal cortex. The order of each arm will be counterbalanced. The four-session duration of the proposed intervention was informed by our past work pairing sensorimotor cortical stimulation with the same serial targeting task to be employed here. A three-week break between study arms will be employed to minimize carry over effects between each arm of the study. Therefore, total duration of the study from enrollment to completion

[figure not shown]

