The statistical approach and power analyses were developed in consultation with the Center for Statistical Consulting and Research at the University of Michigan. For Specific Aim 1 (**Determine whether cTBS over contralesional dorsolateral prefrontal cortex prior to motor practice enhances motor learning post-stroke**) the primary outcome metric will be response time during random reaches. The extent of sensorimotor procedural knowledge will be assessed using an Arm (active-cTBS, sham-cTBS) x Session (Session 2, Session 6) repeated measures ANOVA. The extent of procedural knowledge relating to the larger movement sequence will be assessed using a Arm (active-cTBS, sham-cTBS) x Sequence (Random, Repeated) x Session (Session 2, Session 6) repeated measures ANOVA. As a secondary assessment, the rate of procedural learning will be assessed for each measure by including Sessions 3, 4 and 5 as levels of the factor Session. An Arm (active-cTBS, sham-cTBS) x Session (Session 1, Session 6) repeated measures ANOVA will be used to assess time to complete the Jebsen-Hand Function Test

For Specific Aim 2 (**Determine the effects of cTBS over dorsolateral prefrontal cortex upon motor networks**) two separate sets of analyses will be performed. First, separate Arm (active-cTBS, sham-cTBS) x Hemisphere x Time (Session 1, Session 6) repeated measures ANOVA will be performed to assess change in intracortical motor networks (recruitment curves, short-latency afferent inhibition) across study arm. Motor evoked potential amplitude will be the dependent variable. Arm x Hemisphere x Time interactions will be decomposed using separate Arm x Time repeated measures ANOVAs for each Hemisphere.

Second, to assess changes in intercortical neural networks group level maps for each identified component in the independent component analysis will be assessed using separate Arm x Sequence random-effects analysis for Session 1 and Session 6. Statistical threshold will be set to $p < 0.05$ and corrected for multiple comparisons using the false discovery rate.

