Targeted enrollment for Aim 1 (Behavior) and Aim 2 (Motor networks) is 16 participants. This number was derived using effect sizes from our previous work. We observed effect sizes (partial η^2) for two-way repeated measures Stimulation Site x Session interactions of 0.135 (M1-cTBS vs. Control) and 0.107 (S1-cTBS vs. Control) when comparing response time from early practice to a delayed retention test. Brodie et al. observed effect sizes for motor and sensory improvements pre- to post an S1-5Hz repetitive TMS intervention that ranged between medium (partial $\eta^2 = 0.06$) to large (partial $\eta^2 > 0.16$). Based upon these effect sizes, the targeted enrollment that provides a power of 0.80 at an alpha level of 0.05 with a correlation of 0.7 among the repeated measures is between 5 and 12 participants (G*Power). These numbers are consistent with previously published work using similar cross-over designs to investigate the efficacy of M1 non-invasive brain stimulation interventions upon both behavior and M1 physiology post-stroke (i.e. recruitment curves and short-latency- afferent inhibition). In these studies sample sizes range from 6-16 stroke patients. To

Study Title: Modulating interaction of motor learning networks in rehabilitation of stroke

account for effect sizes within the lower range of our estimates, overestimates of the correlations between the different levels in our repeated measures design as well as experimental mortality (see **Potential Problems and Alternative Strategies**), we will target 16 individuals.

With respect to the measures of resting state functional connectivity (Aim 2), the majority of work post-stroke has been aimed at determining differences in network functional connectivity compared to non-stroke control individuals. To our knowledge, no studies have assessed changes in resting state connectivity across an intervention similar to that proposed here. The closest approximation is a longitudinal study looking at functional connectivity between ipsilesional and contralesional M1 post-stroke. This study (n=12 patients) demonstrated significant differences between 1, 3 and 6 months post-stroke. Therefore, 16 individuals should be sufficient to detect any changes in functional connectivity associated with our intervention.

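### The plan says 16 participants suffice to detect any connectivity change, but gives no supporting calculation; 16 completers give 80% power only from a standardised within-person effect of about 0.75

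*Combined protocol and SAP*

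**What the plan says.** All references are to the combined protocol and SAP, mainly its section Statistical Analyses and Power.

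- **Sample size.** "Targeted enrollment for Aim 1 (Behavior) and Aim 2 (Motor networks) is 16 participants". Under Design, participants "will serve as their own matched control in a cross-over design".
- **Calculation shown.** The only computed range, 5 to 12 participants, assumes "a power of 0.80 at an alpha level of 0.05 with a correlation of 0.7 among the repeated measures". Its effect sizes come from response time and from motor and sensory improvement, not from connectivity.
- **Connectivity.** The plan states that it knows of no study of connectivity change across a similar intervention. As the nearest available evidence it takes a longitudinal study of connectivity between the two primary motor cortices: "This study (n=12 patients) demonstrated significant differences between 1, 3 and 6 months post-stroke". From this it concludes that "16 individuals should be sufficient to detect any changes in functional connectivity associated with our intervention".
- **Connectivity analysis.** Group maps for each identified component are analysed by Arm x Sequence, separately at Session 1 and Session 6, with p < 0.05 "corrected for multiple comparisons using the false discovery rate".

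**The concern.** A significant result in 12 patients shows that one effect was found once. It does not give the power for a different effect. The documents themselves show how the two settings differ:

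- The cited study covers 1 to 6 months after stroke. This trial enrols from more than 3 months after stroke, and each arm lasts at most three weeks.
- The cited study concerns one connection. This trial examines every network found by the independent component analysis.
- The cited result is a change over time. A change attributable to the intervention requires a comparison of active with sham stimulation.

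For any fixed sample size, power falls towards alpha as the effect shrinks, so no sample size can detect every change. If the sentence is taken at face value, a null connectivity result could be read as evidence that stimulation has no network effect. Unlike Aim 3, Aim 2 is not labelled exploratory, so nothing else in the plan tempers that reading.

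**Working it through.** **1. The plan's own figures.** The connectivity statement has no inputs, so there is nothing to reproduce. The neighbouring behavioural range can be checked with the G*Power default formula for a repeated-measures F test:

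- noncentrality λ = f² · n · m / (1 − ρ), with f² = η² / (1 − η²), m = 4 cells, ρ = 0.7, and 1 and n − 1 degrees of freedom;
- at partial η² = 0.06, n = 12: f² = 0.06 / 0.94 = 0.0638, λ = 0.0638 × 12 × 4 / 0.3 = 10.2, power 0.83, so 12 suffice;
- at 0.107 the formula gives 8, at 0.135 and 0.16 it gives 6, and at 0.18 it gives 5.

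This agrees with the stated 5 to 12, but it says nothing about connectivity.

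**2. Detectable effect for connectivity.** Any one-degree-of-freedom within-person contrast reduces to a one-sample test on one number per person. Let dz be the mean of that number divided by its SD. Then λ = n · dz², with 1 and n − 1 degrees of freedom. Alpha is two-sided 0.05 (a 1-df F test is two-sided), and target power is 0.80.

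For n = 16 the critical F(1, 15) is 4.54. Power reaches 0.80 at dz = 0.749, where λ = 16 × 0.749² = 8.98.

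| Completers | dz for 80% power |
|---|---|
| 16 | 0.75 |
| 14 | 0.81 |
| 12 | 0.89 |

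The plan gives no dropout rate, so 14 and 12 are illustrations.

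**3. Power at smaller effects, before correction.**

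| dz | Power at n = 16 | n for 80% power |
|---|---|---|
| 0.2 | 12% | 199 |
| 0.3 | 20% | 90 |
| 0.5 | 46% | 34 |
| 0.8 | 85% | 15 |

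**4. Raw units.** These depend on the contrast and on a correlation that the plan does not give for connectivity. Assume equal variances and one common correlation ρ among the measurements.

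- Difference in change between arms: dz × √(4(1 − ρ)). At ρ = 0.7 this is 0.749 × √1.2 = 0.82 SD. At ρ = 0.5 it is 0.749 × √2 = 1.06 SD. At ρ = 0.3 it is 0.749 × √2.8 = 1.25 SD.
- Active versus sham at one session only: dz × √(2(1 − ρ)). At ρ = 0.7 this is 0.749 × √0.6 = 0.58 SD.

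**5. Multiplicity.** The plan does not say how many tests the false discovery rate correction covers. Purely as an illustration, if the strictest step were 0.05/3 = 0.0167, the detectable dz at n = 16 would rise to 0.90.

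**The case against.** **The contrast.** An arm-by-session connectivity test is not what the plan specifies; it analyses each session separately. This stands for raw units: 0.82 SD belongs to a difference of two changes, against 0.58 SD for a single-session arm comparison at the same correlation. It also undermines any power figure carried over from the cited study. Suppose that study had exactly 80% power (dz 0.889 at n = 12) and the same raw change occurred in the active arm only. Power here would then be 65% for a difference of changes but 91% for a single-session contrast; for half that change, 22% or 38%. No such figure can be relied on until the contrast is fixed. The dz of 0.75 is unaffected, because it applies to either contrast.

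**Stronger readings that the documents do not support.**

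- A reader might infer that only large effects are detectable. That depends on the scale. A dz of 0.75 is just under the common 0.8 cut-off. As an ANOVA would report it, the corresponding partial η² is about 0.36. In the G*Power default metric at correlation 0.7, f² = 0.749² × 0.3 / 4 = 0.042, so η² is about 0.04, below the 0.06 that the plan calls medium.
- A reader might take the cited study to be one of natural recovery. The plan calls it only longitudinal, and openly offers it as the closest evidence available.
- A reader might treat correction over three networks as planned. Three are named, but others may be added, and the correction may instead run within each map.
- A reader might conclude that the plan intends to read a null as no effect, or that 16 is too few. It says neither, and a sample of this size can be legitimate for early work.

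**Dropout.** The plan offers a mixed model for patients who complete only one arm. That keeps their data, but they contribute no within-person comparison between arms.

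**Conclusion.** The claim is unsupported and cannot be true as worded. It is an over-stated sample-size justification, not an arithmetical error, since no connectivity calculation was made. With 16 completers, 80% power begins at dz of about 0.75. An effect of dz 0.5 would be missed slightly more often than found, and one of 0.3 missed about four times in five.

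These figures assume a one-degree-of-freedom within-person contrast, approximate normality, two-sided 0.05, complete data and no multiplicity correction. Dropout or correction makes the detectable effect larger. Whether the true effect lies above or below 0.75 cannot be judged from the documents.

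**What to change.** 1. Replace the sentence with wording such as: *16 completers give 80% power for a standardised within-person effect (dz) of about 0.75 before correction for multiple comparisons; smaller changes may be missed, and the detectable effect is larger after correction or dropout.*
2. Reconcile the sample-size text with the Aim 2 connectivity analysis, so that the detectable effect refers to the contrast that will be tested. At present the analysis is Arm x Sequence at each session, with no arm-by-session test.
3. If raw units are given, show a range over assumed correlations. For a difference in change between arms: 0.82 SD at 0.7, 1.06 at 0.5 and 1.25 at 0.3.
4. If a corrected figure is quoted, state the family of tests that it assumes and label it illustrative.
5. Report connectivity effects with confidence intervals, and state that non-significance will not be interpreted as absence of effect.

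The cost is a revised sample-size paragraph and a clarified connectivity analysis. No extra participants, scans or visits are needed. The stated capability becomes more modest.
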